## 2 Methods

### 2.1 Trial overview, ethical consideration, and patient recruitment

This study is an ongoing, single-center, cross-sectional observational clinical trial. The subjects were selected for observation and subsequent analysis for key biomarkers such as blood glucose, Urine Albumin-to-Creatinine Ratio(UACR), and renal function. Blood, urine, feces, and moss on the tongue samples were collected from the subjects and stored for subsequent analysis. The study protocol was approved by the Ethics Committee of the First Affiliated Hospital of Hunan University of Traditional Chinese Medicine in accordance with the relevant ethical standards. The study is currently being conducted at the First Affiliated Hospital of Hunan University of Traditional Chinese Medicine and involves four groups of participants: type 2 diabetic kidney disease (DKD), type 2 diabetes mellitus (T2DM), chronic kidney disease (CKD), and healthy human. Subjects will be recruited from inpatients or outpatients of the Department of Endocrinology and the Department of Nephrology of the First Affiliated Hospital of Hunan University of Traditional Chinese Medicine. Additionally, healthy human subjects will be recruited from the general public through printed advertisements, invitations, etc. The total number of individuals proposed to be recruited in the four groups is 720.

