### 2.2 Study outcomes

**Primary outcome:** By employing a combination of microbiomic and metabolomic technologies, we conducted a comprehensive analysis of the intestinal flora and serum metabolic profiles associated with DKD. This approach enabled us to identify potential enterogenous disease markers of DKD and to investigate the metabolic profiles that may be linked to disease progression.

**Secondary outcome:** The objective of this study is to analyze the interaction between intestinal flora and intestinal-derived metabolites in the disease process of DKD. Additionally, the aim is to provide new disease diagnostic strategies and progression risk assessment indicators for diabetic nephropathy, which can be applied to early identification, precise diagnosis, and prognosis of the disease.

**Exploratory outcomes :** In accordance with the test results, each group will select four to six remaining fecal samples as the donor source for allogeneic fecal bacteria transplantation. Subsequently, the correlation between intestinal flora and enteric metabolites in diabetic nephropathy will be investigated through the method of human-mouse allogeneic flora transplantation.

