### 2.4 Study procedures

#### 2.4.1 Questionnaire to collect information

(1) General items: name, gender, age, BMI, education level, labor intensity, dietary preferences, etc;

(2) TCM symptoms, tongue and pulse;

(3) Clinical information: disease duration, other complications (e.g., diabetic peripheral neuropathy, diabetic retinopathy, diabetic cardiomyopathy, etc.), concomitant diseases (hypertension, coronary artery disease, hyperlipidemia, cerebrovascular disease, and hyperuricemia, etc.), past medical history, history of smoking, alcohol, family history, and history of drug use.

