#### 2.4.2 Outcome Measures

Indicators of safety: Physical examination (including general condition, blood pressure, heart rate, heart rhythm, body temperature, respiratory rate, etc.) was

performed before taking the samples to assess the basic condition of the subjects.

**Primary Outcome Measures :** Urine Albumin-to-Creatinine Ratio(UACR), Estimated Glomerular Filtration Rate(eGFR),blood urea nitrogen(BUN), serum creatinine(Scr), fasting blood glucose(FBG), Glycosylated Hemoglobin, Type A1C(HbA1c), glucosylated serum protein(GSP) , etc. Test data were obtained from test results conducted within one month of enrollment for the purpose of evaluation.

**Secondary Outcome Measures:** 16S ribosomal DNA(16S rDNA) identification, metagenomic Next Generation Sequencing, Non-targeted and targeted Metabolomics technology detection , etc.

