## 2.5 Data analysis

SPSS 26.0 will be applied for statistical analysis of clinical indicators. Data that exhibited a normal distribution were expressed as the mean  $\pm$  standard deviation(  $x \pm s$ ), and an independent samples t-test was employed for comparison between two groups. Data that did not conform to a normal distribution were expressed as the median and interquartile spacing [M(IQP)], and a Mann-Whitney rank-sum test (U test) was used for comparison between two groups. In the case of count data, these were expressed as frequencies or percentages. In the event of unordered categorical count data, comparisons between two groups were performed using either the four-cell table or the column table  $c^2$  test. The Pearson  $c^2$  test or Fisher's exact probability method was employed in accordance with the sample size and the size of the theoretical frequency. In the case of ordered categorical count data, comparisons between two groups were performed using the U test. A two-sided test was employed for the normality test and variance chi-square test, with an alpha level of 0.1. This resulted in the rejection of the original hypothesis, indicating that the data are not normally distributed or that there is no significant variance. For other significance tests, an alpha level of 0.05 was used, leading to the rejection of the original hypothesis and the conclusion that the difference is statistically significant.

An integrated correlation analysis will be performed using a variety of analytical techniques, including intestinal flora species diversity analysis, Spearman's correlation analysis, network analysis, Procrustes analysis, MaAsLin analysis, ERMANOVA analysis, random forest analysis of differential intestinal flora with differential metabolites between groups, and efficacy evaluation.

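### The secondary outcome promises progression-risk indicators and prognosis, but the study is cross-sectional and observes no progression; that part of the aim should become association with current DKD severity

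*Combined protocol and SAP*

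**What the plan says.** All references are to the combined protocol and SAP.

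- Section 2.2, secondary outcome: after the interaction of flora and metabolites, the study is to provide new diagnostic strategies and "progression risk assessment indicators for diabetic nephropathy, which can be applied to early identification, precise diagnosis, and prognosis of the disease". The sentence is not hedged. The primary outcome in the same section also mentions progression, but only as something the metabolic profiles may be linked to.
- Section 2.1: the study is a "single-center, cross-sectional observational clinical trial" with four groups (DKD, T2DM, CKD, healthy) and 720 subjects in total. The split by group is not given.
- Section 2.4.1: one questionnaire, covering "General items: name, gender, age, BMI, education level, labor intensity, dietary preferences" and other items; "Clinical information: disease duration, other complications"; and "family history, and history of drug use".
- Section 2.4.2: UACR, eGFR and other laboratory measures, with this timing: "Test data were obtained from test results conducted within one month of enrollment for the purpose of evaluation".
- Section 2.5: two-group tests for the clinical indicators, with alpha 0.05 for significance tests other than those of normality and variance. For the omics data there is a list of methods that includes "correlation analysis, network analysis, Procrustes analysis, MaAsLin analysis, ERMANOVA analysis". No analysis population, severity variable, covariates or multiplicity rule is given for any of them.

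**The concern.** Progression is change over time and prognosis is a statement about a later outcome. Both need at least two points in time per person, or an event after baseline. The plan provides one.

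What is at stake is how a positive finding will be read. Suppose a metabolite is higher in DKD subjects with lower eGFR. One explanation is that it drives or foretells decline. Another is that it accumulates because the kidney already clears less of it. One cross-sectional sample shows the same association in both cases. With the secondary outcome as worded, the result could be reported as a progression-risk indicator, and the plan contains nothing that would expose the error.

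**Working it through.** The plan has no figure to reproduce on this point. The main check is to set the aim against what is collected.

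**Step 1. Look for an observation of progression.**
- Design (2.1): cross-sectional.
- Laboratory values (2.4.2): one window, within one month of enrolment. No repeat UACR or eGFR and no eGFR slope.
- Events: no kidney failure or other progression event is defined as an outcome.
- Disease duration (2.4.1): a single retrospective item. It says how long the disease has been present and supplies no earlier measurement of kidney function.
- Analysis (2.5): no longitudinal, time-to-event or prognostic model.
- Discussion (3): its closing mention of follow-up concerns later treatment strategies, not participants.
- Exploratory outcome (2.2): transplantation of human flora into mice. It observes no patient's progression.

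The number of progression events or repeat kidney measurements that the described design yields is zero, whatever the sample size.

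**Step 2. What a cross-sectional association implies about the future (illustration).** Let r1 be the correlation of a marker with current severity and r2 the correlation of current severity with future decline. The correlation of the marker with future decline can then lie anywhere in

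r1·r2 ± √[(1 − r1²)(1 − r2²)].

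Both inputs are assumed; the documents give neither.
- r1 = 0.34, r2 = 0.3: 0.102 ± √(0.8844 × 0.91) = 0.102 ± 0.897, that is −0.80 to 1.00.
- r1 = 0.34, r2 = 0.5: 0.170 ± √(0.8844 × 0.75) = 0.170 ± 0.814, that is −0.64 to 0.98.

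These are limits in the population, not confidence intervals, so more subjects do not narrow them.

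**Step 3. What a severity analysis could detect (illustration).** Assumptions: 180 DKD subjects (720/4, an equal split that the plan does not state), 10 covariate terms, two-sided tests, 80% power. The detectable partial correlation by Fisher z is

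r = tanh[(z for alpha + 0.842) / √(n − 10 − 3)].

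- Single test at 0.05: tanh(2.802 / √167) = tanh(0.217) = 0.21.
- Bonferroni over 400 tests (200 assumed markers × 2 severity variables): tanh[(3.836 + 0.842) / √167] = tanh(0.362) = 0.35.
- Bonferroni over 2,000 tests (1,000 assumed markers × 2): tanh[(4.215 + 0.842) / √167] = tanh(0.391) = 0.37.

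With 120 DKD subjects the same formula (√107) gives 0.26, 0.42 and 0.45. With 240 (√227) it gives 0.18, 0.30 and 0.32. Bonferroni is a conservative stand-in for the Benjamini-Hochberg control proposed under the fix. These figures show only that the replacement analysis is feasible for moderate associations; they do not measure the defect.

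**The case against.** The strongest reply is that the sentence states an aim, not an estimand. No prognostic model is specified that could be wrong, and the Discussion presents the work as a correlation analysis in search of markers. The primary outcome and the group comparisons are untouched. This stands as far as it goes: the defect lies in the conclusion the plan licenses, not in a faulty calculation. But the sentence is the stated secondary outcome, and it says the indicators can be applied to prognosis. The Discussion also speaks of disease onset and risk factors, so it does not clearly narrow the aim.

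A second reply is that the T2DM and DKD groups represent successive stages, or that the mouse experiment could settle direction. Comparing different people at one time does not show who will progress. The mouse work may bear on mechanism but gives no patient prognosis.

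Two stronger readings are tempting, and the documents do not support them.
- A reader might infer that the study can show nothing beyond association with current severity. With four groups it can also address group differences and diagnostic discrimination, such as DKD against T2DM or CKD, so the diagnostic part of the secondary outcome is not ruled out.
- A reader might infer that the random forest is a classifier whose accuracy will be inflated by feature selection on all subjects. Section 2.5 lists only "random forest analysis of differential intestinal flora with differential metabolites between groups, and efficacy evaluation", within an integrated correlation analysis. It states neither a classifier role nor a selection rule, and the matter is separate from progression.

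**Conclusion.** The concern holds for the progression and prognosis wording of the secondary outcome, with high confidence, because it follows from the plan's own description and needs no outside figure. The size is categorical: that part of the aim cannot be met by this design with 720 subjects or any other number. The correlation limits in step 2 and the detectable correlations in step 3 rest on assumed inputs (correlations, group size, marker counts) and serve only as illustration.

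The data remain usable, and the other aims are unaffected by the lack of follow-up. The plan should be changed before analysis, and the study is still ongoing. The model proposed under the fix is one reasonable specification among several, and the high confidence does not extend to its details.

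**What to change.** 1. **Section 2.2.** In the secondary outcome, replace the progression-risk and prognosis wording with: markers associated with current DKD severity (hypothesis-generating for progression). Keep the diagnostic aim. In the primary outcome, change the tentative reference to progression to association with current disease severity, so that the two agree.
2. **Section 2.5.** Add a severity analysis within the DKD group. Staying within one group avoids circularity if UACR or eGFR help define the groups; the cited diagnostic criteria are not reproduced in the plan. Use the listed MaAsLin for taxa and the same linear model for log-transformed serum metabolites, with log-UACR and eGFR as severity variables. Adjust for covariates already collected, for example age, sex, BMI, disease duration, drug use and dietary preferences. Control the false discovery rate by Benjamini-Hochberg at 5% over all marker-by-severity tests, in place of an unadjusted alpha of 0.05. The exact covariate list and the taxon filter and transformation are for the sponsor's statistician to fix before the data are analysed.

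**Cost.** No new data or samples. The added analysis is modest but real: MaAsLin is listed, whereas a within-DKD severity model is not. The claims become narrower, and the associations can still reflect reverse causation, which the report should say. Keeping the progression aim would instead require follow-up with a defined endpoint, which is a new study phase and is not costed here.

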### 2.3 Study population

This study primarily recruited Type 2 diabetic kidney disease (DKD), Type 2 diabetes mellitus (T2DM), Chronic kidney disease (CKD), and healthy human.

#### 2.3.1 Patient inclusion criteria:

- (1) Age  $\geq 18$  years old and  $\leq 75$  years old, gender is not limited.
- (2) Complete demographic data.

(3) Meet the diagnostic criteria of the Chinese Guidelines for the Prevention and Treatment of Diabetic Kidney Disease (2021 edition), the Chinese Guidelines for the Prevention and Treatment of Type 2 Diabetes Mellitus (2020 edition), and the Guidelines for the Screening, Diagnosis, Prevention and Treatment of Chronic Kidney Disease (2017 edition).

(4) The patient is informed of the study as approved by the ethics committee.

#### 2.3.2 Healthy population inclusion criteria:

(1) The patient has no known history of infection or risk factors including HIV hepatitis B or C virus syphilis etc. and no current systemic infection;

(2) No obesity (body mass index  $>30$ ) and/or diabetes no history of chronic kidney disease;

(3) Approved by the ethics committee patients were informed about the study.

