#### 2.3.3 Exclusion criteria:

(1) A history of infection or other acute disease within one month prior to enrollment.

(2) People who are in a state of stress.

(3) Other unstable chronic diseases;

(4) A history of acute and chronic gastrointestinal diseases, including acute gastroenteritis, functional gastrointestinal diseases, inflammatory bowel disease, celiac disease, and other chronic gastrointestinal diseases.

(5) Individuals who have received systemic antibiotics, immunosuppressants, chemotherapy, or chronic treatment with proton pump inhibitors within the past three months will be excluded from participation.

(6) Pregnant or lactating women.

(7) Individuals who have participated in other drug clinical trials within the past three months.

(8) Individuals who suffer from mental illness, intellectual disability, confusion, or other conditions that may interfere with their ability to cooperate with the completion of relevant information collection will also be excluded.

In order to ensure the rigor and reliability of the study, subjects who met one or more of the aforementioned criteria were excluded.

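### The age range of 18 to 75 binds patients only, and with no matching and no named covariates the DKD-versus-healthy comparisons are open to confounding by age, and also by sex and BMI

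*Combined protocol and SAP*

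**What the plan says.** Section 2.3.1 opens the patient criteria with "Age $\geq 18$ years old and $\leq 75$ years old" and places no restriction on sex. The separate list in section 2.3.2, headed "Healthy population inclusion criteria", has three items. The first requires "no known history of infection or risk factors including HIV hepatitis B or C virus syphilis etc. and no current systemic infection". The second rules out a BMI above 30, diabetes and a history of chronic kidney disease. The third concerns information about the study. None of them mentions age.

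The exclusions in section 2.3.3 apply to everyone: "subjects who met one or more of the aforementioned criteria were excluded". They include "A history of infection or other acute disease within one month prior to enrollment", other unstable chronic diseases, and "Individuals who have received systemic antibiotics, immunosuppressants, chemotherapy, or chronic treatment with proton pump inhibitors within the past three months". They contain no age or BMI rule.

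Under section 2.1, patients come from two hospital departments, while "healthy human subjects will be recruited from the general public through printed advertisements, invitations, etc". No matching is described. Section 2.4.1 records age, gender, BMI and past medical history. Section 2.5 plans t-tests, Mann-Whitney tests and chi-square or Fisher tests between pairs of groups for clinical indicators. For flora and metabolites it lists MaAsLin, ERMANOVA, random forest and other methods, without naming a covariate for any of them.

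**The concern.** The primary outcome in section 2.2 is to identify gut-derived markers of DKD. Healthy subjects are one of the three reference groups. Volunteers who answer an advertisement may differ in age and sex from hospital patients with DKD, and by rule they cannot have a BMI above 30. A flora or metabolite feature that tracks age, sex or BMI could then separate the two groups and be put forward as a DKD marker without any relation to the disease.

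Three tools could prevent this: parallel entry rules, matching, or adjustment in the analysis. The plan as written commits to none of them for the DKD-versus-healthy contrast. Section 2.2 also takes four to six fecal donors from each group for the transplantation experiment, so an imbalance could carry over into that work.

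**Working it through.** The plan gives no power calculation, effect size or age distribution, so there is no figure of its own to reproduce. The check has two parts.

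**Entry rules side by side**

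| Rule | DKD, T2DM, CKD | Healthy | Source |
|---|---|---|---|
| Age | 18 to 75 | none | 2.3.1, 2.3.2 |
| BMI above 30 | allowed | barred | 2.3.2 |
| Known history of HIV, hepatitis B or C, syphilis, or risk factors | no bar | barred | 2.3.2 |
| Infection within one month | barred | barred | 2.3.3 |
| Systemic antibiotics within three months | barred | barred | 2.3.3 |
| Sex | no restriction | no restriction stated | 2.3.1, 2.3.2 |

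Age, BMI and older or chronic infection are therefore treated differently in healthy subjects. Sex is not. It can become unbalanced only because the groups are recruited by different routes without matching.

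**Illustration of size**

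The only input from the documents is the two-sided alpha of 0.05 (section 2.5). Section 2.1 gives a total of 720 but no split. Equal groups, 720 / 4 = 180, are an assumption. Assume also that the feature has no true relation to DKD and that the test is unadjusted.

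- Bias in SD units = (age gap in decades) × (change in SD per decade). An assumed 10-year gap and 0.1 to 0.2 SD per decade give 1 × 0.1 = 0.1 to 1 × 0.2 = 0.2 SD.
- Standard error = √(2/180) = 0.1054 SD.
- False-positive rate = Φ(bias/SE − 1.96) + Φ(−bias/SE − 1.96).
- Bias 0.1: 0.1/0.1054 = 0.949, and the rate is 15.8%.
- Bias 0.2: 0.2/0.1054 = 1.897, and the rate is 47.5%.

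| Assumed bias (SD) | 180 per group | 100 per group |
|---|---|---|
| 0.1 | 15.8% | 10.9% |
| 0.2 | 47.5% | 29.3% |
| 0.4 (for example a 20-year gap at 0.2 SD per decade) | 96.7% | 80.7% |

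A second set of assumptions takes bias as the age–feature correlation times the age gap in SD. Correlations of 0.1 to 0.3 and gaps of 0.25 to 1.0 SD give a bias of 0.025 to 0.30 SD and rates of 5.6% to 81% at 180 per group.

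For the infection-history bar, bias = (proportion of DKD patients with such a history) × (shift in SD). With 2% to 10% and 0.3 to 0.5 SD (assumed), this is 0.006 to 0.05 SD, and the rate is 5.0% to 7.6%, close to nominal. At 10% and a shift of 1 SD the bias is 0.10 SD and the rate 15.8%, but that is the extreme corner.

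**The case against.** Several counter-arguments have force.

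- **Infection.** A reader might infer that only healthy subjects face an infection bar. The documents do not support that: recent infection and recent systemic antibiotics are excluded in all groups, as are other unstable chronic diseases. Only the bar on older or stable chronic infection and on risk factors is specific to healthy subjects, and its likely effect is small.
- **Risk or fact.** A reader might infer that the reported differences do reflect age. No age distribution is given, so the documents show only that nothing prevents this.
- **Other comparators.** T2DM and CKD patients are held to the same entry rules as DKD patients, and those contrasts bear on whether a marker is specific to DKD. Section 2.2 does not name the healthy group as the key reference. This limits the point to DKD versus healthy.
- **Which analysis.** The unadjusted tests are planned for clinical indicators. Flora and metabolite features go to methods that include MaAsLin, which can take covariates. For those features the gap is that no covariates are named, and the rates above apply only if the analysis is in effect unadjusted.
- **What the missing limit causes.** A gap of 10 or 20 years in mean age can arise with both groups inside 18 to 75. The calculated bias therefore cannot be attributed to the missing limit, and adding the limit alone would not remove it.

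All five stand as limits on the claim. None supplies the missing matching or adjustment.

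**Conclusion.** The point holds as a design and analysis gap. Patients have an age range and healthy volunteers do not; healthy volunteers have a BMI bar and a chronic-infection bar that patients do not. Neither matching nor prespecified adjustment makes up for this, so DKD-versus-healthy differences may be confounded by age, and also by sex and BMI. Age leads, and the infection asymmetry is secondary.

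The size cannot be derived from the documents. On assumptions of 180 per group, no true effect, an unadjusted test and an age-related bias of 0.1 to 0.2 SD, the false-positive rate per feature is 16% to 48% instead of 5%. Smaller biases bring it close to nominal, and larger ones make a false finding likely. The correction is cheap relative to that range and should be made while recruitment continues.

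**What to change.** 1. Add the range of 18 to 75 years to section 2.3.2.
2. For the remaining recruitment, frequency-match healthy subjects to the DKD group by 10-year age band and sex.
3. In section 2.5, replace the unadjusted group comparisons with regression models adjusted for age and sex. Name the same covariates for MaAsLin and for the permutational analysis (written ERMANOVA).
4. Add a sensitivity analysis that also adjusts for BMI. Because no healthy subject may have a BMI above 30, it extrapolates for patients above that value, and the report should say so.
5. Do not add an infection-history exclusion for patients. The study is already enrolling, and a new exclusion would put earlier and later patients under different rules. Use the recorded past medical history in a sensitivity analysis that omits subjects with known chronic infection.

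Age, gender, BMI and medical history are already collected under section 2.4.1, so no new measurement is needed. The covariate adjustment also covers those already enrolled. The cost is a short amendment, slightly slower recruitment of healthy subjects and some extra analysis work.

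### Healthy controls are cleared of kidney disease by history only and of diabetes by no stated test; the planned laboratory results do not decide eligibility, so undiagnosed cases can stay in the reference group

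*Combined protocol and SAP*

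**What the plan says.** Section 2.3.2(2) sets the metabolic and renal conditions for a healthy volunteer. After a body-mass-index limit it continues "and/or diabetes no history of chronic kidney disease". The kidney part concerns history. The diabetes part concerns absence of the disease, with no test or threshold named.

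Section 2.1 gives the source: "healthy human subjects will be recruited from the general public through printed advertisements, invitations, etc". Patients are held to a different standard in 2.3.1(3), which begins "Meet the diagnostic criteria of the Chinese Guidelines for the Prevention and Treatment of Diabetic Kidney Disease (2021 edition" and goes on to name guidelines for type 2 diabetes and for chronic kidney disease. In 2.3.3 the nearest exclusion is "Other unstable chronic diseases".

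The relevant tests are planned. Section 2.1 says subjects are selected for observation and "subsequent analysis for key biomarkers such as blood glucose, Urine Albumin-to-Creatinine Ratio(UACR), and renal function", with no exemption for the healthy group. Section 2.4.2 lists as primary outcome measures "Urine Albumin-to-Creatinine Ratio(UACR), Estimated Glomerular Filtration Rate(eGFR),blood urea nitrogen(BUN), serum creatinine(Scr), fasting blood glucose(FBG", followed by HbA1c and glycated serum protein. On timing and purpose it says: "Test data were obtained from test results conducted within one month of enrollment for the purpose of evaluation". No section says that these results decide who counts as healthy, or what happens to a volunteer whose results are abnormal.

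**The concern.** Early kidney disease and early diabetes can be present without a diagnosis, so a history-based rule cannot exclude them. As the kidney rule is written, a volunteer with no known kidney disease but a clearly abnormal UACR or eGFR qualifies as healthy and remains so after the result is known. The 2.3.3 exclusion for unstable chronic disease does not reach a silent, stable condition.

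The study looks for gut-derived markers of DKD and, in 2.2, hopes to use them for early identification and diagnosis. Silent cases among the controls would pull DKD-versus-healthy differences toward zero. A marker that correctly detects a silent case would also be scored as a false positive. The tests that could settle the matter are already in the plan; what is missing is a rule that uses them.

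**Working it through.** **Reading the sections together.**

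- Kidney disease in controls: history only (2.3.2(2)).
- Diabetes in controls: must be absent, method of confirmation not stated (2.3.2(2)).
- Patients: guideline diagnostic criteria (2.3.1(3)).
- Exclusions: none catches silent, stable disease (2.3.3).
- UACR, eGFR, FBG, HbA1c: collected for evaluation (2.4.2), not tied to eligibility or the analysis set.

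The gap follows from the text alone. The arithmetic below only indicates its possible size.

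**Inputs.** Section 2.1 states: "The total number of individuals proposed to be recruited in the four groups is 720". The plan gives no split, effect size, standard deviation or power, so the 720 cannot be reproduced. Assumed here: equal groups, 720/4 = 180; a share p of 5% to 15% of controls misclassified; each of them fully resembling a DKD case; unit standard deviation within groups. The two-sided alpha of 0.05 is from 2.5.

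**Number misclassified.** 180 × 0.05 = 9; 180 × 0.15 = 27.

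**Mean difference.** Observed difference = (1 − p) × d, where d is the true standardized difference. The shrinkage is therefore 5% to 15%. Ignoring the small rise in variance, the sample needed for the same power grows by 1/(1 − p)²: 1/0.95² = 1.11 and 1/0.85² = 1.38.

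**Power.** Control variance = 1 + p(1 − p)d²; s² is the mean of the two group variances. Power = Φ[(1 − p)d / (s√(2/180)) − 1.96].

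| p | misclassified | d = 0.3 seen as | power | n per group for 80% | d = 0.5 seen as | power |
|---|---|---|---|---|---|---|
| 0 | 0 | 0.300 | 81.2% | 175 | 0.500 | 99.7% |
| 5% | 9 | 0.285 | 77.1% | 194 | 0.475 | 99.4% |
| 10% | 18 | 0.270 | 72.5% | 217 | 0.450 | 98.9% |
| 15% | 27 | 0.255 | 67.4% | 243 | 0.425 | 97.9% |

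The exact sample-size ratio at 5% is 194/175 = 1.11, in line with the approximation.

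**Discrimination.** Observed AUC = (1 − p) × AUC + 0.5p. A true AUC of 0.80 is seen as 0.95 × 0.80 + 0.025 = 0.785 at 5%, and as 0.85 × 0.80 + 0.075 = 0.755 at 15%.

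**Specificity.** Take a marker with assumed specificity 0.90 and sensitivity 0.80. If silent cases are marker-positive as often as DKD cases, apparent specificity = (1 − p) × 0.90 + p × 0.20. This gives 0.855 + 0.010 = 0.865 at 5% and 0.765 + 0.030 = 0.795 at 15%. If silent cases behave like true controls on the marker, it is (1 − p) × 0.90 + p × 0.90 = 0.90, with no loss.

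**The case against.** Four arguments limit the point, and all four stand.

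**Diabetes is not cleared by history.** A reader might infer that diabetes, like kidney disease, is excluded only by what the volunteer reports. The text requires its absence, so a volunteer whose study FBG or HbA1c is diagnostic fails the rule as written. For diabetes, only the method of confirmation is missing.

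**Contamination is possible, not shown.** A reader might infer that undiagnosed cases do enter the group. The documents give no prevalence among volunteers and support only that such cases can enter. Section 1 stresses early detection in order to preserve renal function. It does not claim that silent DKD is found among public volunteers without diabetes.

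**The reach is limited.** A reader might infer that the whole DKD signature is distorted. Only analyses that use the healthy group are touched. The comparisons with T2DM and with CKD do not use it, and the calculations show dilution, not distortion in other directions.

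**The figures sit at the upper end.** Silent disease in volunteers may be milder than disease in recruited hospital patients, and much of it may be diabetes alone or non-diabetic kidney disease. A DKD-specific marker should be negative in such people, and would then be scored correctly. Even with full resemblance, a moderate effect loses little: at d = 0.5 and p = 5%, power is 99.4% against 99.7%.

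It could also be said that the investigators will see the laboratory results and act on them. They may, but no rule says so, and removal left to discretion once omics results are known would create a problem of its own.

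**Conclusion.** The concern holds in limited form. By the stated rule, a volunteer with unrecognized kidney disease qualifies as a healthy control and stays one even when the study's own UACR or eGFR is abnormal. The same can happen with diabetes if its absence is not checked. This is more than a missing detail for kidney disease, because following the rule as written gives a weaker reference group than the planned data would allow.

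The direction is dilution of contrasts with healthy controls. The size cannot be fixed from the documents. The figures of 9 to 27 misclassified controls and 5% to 15% shrinkage are upper-end values for each assumed prevalence. They rest on 180 per group and on full resemblance to DKD cases. The apparent specificity of 0.80 to 0.87 applies only if silent cases are marker-positive as DKD cases are. The gap does not invalidate the study, but it should be closed.

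**What to change.** Amend 2.3.2(2) so that healthy status requires the UACR, eGFR, FBG and HbA1c results already planned within a month of enrollment not to meet the diagnostic criteria of the guidelines cited in 2.3.1(3). Section 2.1 describes the study as ongoing, so the rule should cover controls already enrolled as well as future ones. Remove those who fail from the healthy group before any omics data are seen, record how many there were, and report a sensitivity analysis with them included.

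The amendment should also say how a single abnormal value is handled, since whether the cited guidelines need a repeat measurement cannot be checked from these documents.

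The cost is protocol wording and the use of results the plan already lists. The downside is that a few volunteers are lost or must be replaced.
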